### **Sample Characteristics**

Three hundred and thirty SLH residents who are on probation or parole and are HIV+ or at high risk for HIV will be recruited into the study within their first month of entering the SLH. The director of the Sober Living Network in Southern California, [name], states over 60 houses in Los Angeles County accept large numbers of male and female offenders and the vast majority will be willing to participate in the study. This is consistent with our previous study of SLHs, where less than 5% of potential participants declined to participate. Belenko (2006) has documented that criminal justice offenders have very high rates of HIV infection and high risk behaviors. This supports the feasibility of meeting our recruitment goal to enroll HIV+ or high risk individuals. To be parsimonious in our efforts, we will select the 70 houses with the largest number of offenders admitted. Half of the houses (N=35) will be gender specific for men and half (N=35) will be gender specific for women. Stratified random sampling procedures will be used to ensure an equal number of male and female houses within each study condition. Thus, individuals enrolled in houses assigned to the MICM condition will receive that intervention and individuals assigned to the comparison condition will receive SLH services as usual along with a list of referral resources for a wide variety of problems. Risks for contamination of intervention effects on non-intervention offenders are eliminated because of our randomization of houses. These procedures will enable us to reach our target recruitment with an average of only 10.3 residents per house over 3 years of recruitment. We will randomize more houses if we need them to meet our recruitment goals.

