## **D. Procedures**

### **Design Summary**

This study will use a stratified randomization design to assess male (N=165) and female (N=165) offenders on probation or parole who are either HIV+ or at high risk for HIV. Study participants will be recruited from individuals entering selected SLHs in Los Angeles County. Seventy SLHs (35 gender-specific for men and 35 gender-specific for women) that are members of the Sober Living Network will be randomly stratified between MICM (the intervention) and referral resources (the control). Using an “intent to treat model,” we will interview all participants at three time points over a 1-year period: baseline (within one month of entering the house) and 6- and 12-month follow up. The two study conditions will be compared on the primary and secondary outcome measures. Qualitative interviews will be conducted with 13-15 residents in each study condition (N=28) to explore strengths, weaknesses, and potential mechanisms of action of SLHs and MICM.

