## **Research Interviews**

Residents who are interested in participating will attend a research interview that will begin with an assessment of inclusion/exclusion criteria. Those who meet the criteria will be administered the baseline interview after they are consented.

Randomization will occur at the house level, so individuals in houses randomized to the MICM condition will receive that intervention and individuals in houses assigned to the comparison condition will receive SLH services as usual along with a list of referral resources for a variety of problems. Using an “Intent to Treat” design, all participants will be followed up at all of the time points even if they leave the SLH immediately after completion of the baseline interview. Follow-up interview procedures will include updating contact information at each interview as well as at 3 and 9 months. During these interim 3- and 9-month contacts, we will first reach out to participants by phone and, if we were unsuccessful, we would send a letter encouraging them to call us. Those who we were able to speak with would receive a \$5 gift card at the 3-month contact and a \$10 gift card at the 9-month contact. For participants who are difficult to reach we will use tracking methods described by Anglin et al (1996). They include procedures to utilize contact information from respondents’ families and friends and locating participants in jails, prisons, and other institutions. Participants will receive \$30 for the baseline interview and \$50 for interviews at 6- and 12-month follow up. We expect baseline sessions to last 2 hours and follow up sessions to last about 90 minutes. We are using Survey Gizmo as the platform for the interviews, which will require an internet connection for us to access the survey. The connection being used while transferring data between ARG equipment and Survey Gizmo will be protected by a 128-bit encrypted SSL tunnel so as to prevent confidential data from being sniffed. Interviewers will conduct interviews only on ARG laptops, which will be password protected and configured on the ARG secure network.

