Months 1-4	Recruit and train therapists and interviewers, IRB approval, Federal Certificate of Confidentiality, Review instruments and data collection procedures, Complete Procedures Manual and Question-by-Question guidelines, Pilot test interventions and data collection procedures.
Months 5-43	Recruit approximately 8 study participants per month over 38 months. Finish data cleaning for baseline data at month 43.
Months 44-52	Complete all follow up interviews.
Months 53-60	Complete longitudinal analysis of data. Submit papers to addiction and criminal justice journals as well as trade magazines for addiction professionals. Present final analyses to consumers and other stakeholders.

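### The SAP timeline closes follow-up at month 52, 2–3 months before the last 12-month interviews required by the protocol fall due

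*SAP*

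**What the plan says.** The Timeline at the end of the SAP divides 60 months into four rows.

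- Months 1–4: set-up.
- Months 5–43: "Recruit approximately 8 study participants per month over 38 months", followed by "Finish data cleaning for baseline data at month 43".
- Months 44–52: "Complete all follow up interviews".
- Months 53–60: "Complete longitudinal analysis of data", together with papers and presentations.

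The protocol sets the follow-up. Under Design Summary, "we will interview all participants at three time points over a 1-year period", given as "baseline (within one month of entering the house) and 6- and 12-month follow up". Under Research Interviews, "all participants will be followed up at all of the time points", including people who leave the house straight after baseline. Neither document gives late enrollees a shorter follow-up, and neither sets an administrative cut-off.

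The protocol's Sample Characteristics section describes enrolment "over 3 years of recruitment". The SAP's Power Considerations assume 80% contact at 12 months, which gives 132 per group and 264 in total.

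**The concern.** A 12-month interview for the last person enrolled needs 12 months after the end of recruitment. The Timeline leaves 9 or 10, depending on whether the last enrolment is in month 43 or month 42. The two requirements, everyone seen at 12 months and all follow-up finished by month 52, cannot both be met.

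The 12-month interview is the last of three time points in the growth models for H1.1 and H3.1–H3.3. It is also the final interview in the SAP's basic power calculation. If field staff treated month 52 as a hard stop, the latest enrollees would lose that interview for purely administrative reasons. The power section does not say whether its 20% loss allows for this. If staff ignored month 52, the row reserved for the final analysis would open before the data were complete.

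**Working it through.** **Inputs.** From the SAP Timeline: recruitment starts in month 5 and lasts 38 months; the recruitment row is labelled 5–43; follow-up ends in month 52; the analysis row is 53–60. From the protocol's Design Summary and Research Interviews: 12 months of follow-up for all. From the SAP's Power Considerations: 330 participants, 80% contact at 12 months, d = .35, two-sided α = .05.

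**How months are counted.** Counted inclusively, the rows hold 4 + 39 + 9 + 8 = 60 months, so inclusive counting is the natural reading. Thirty-eight months from month 5 are months 5–42; the row label taken inclusively gives 39 months, 5–43. Both are carried through.

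**Calendar.** Last interview due = last enrolment month + 12.

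| Reading | Last enrolment | Last 12-month interview | Past month 52 |
|---|---|---|---|
| 38 months | 42 | 42 + 12 = 54 | 2 months |
| 39 months | 43 | 43 + 12 = 55 | 3 months |

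Reading the labels as points in time gives 5 + 38 + 12 = 55, again 3 months over. The last 6-month interviews fall in month 48 or 49 and do fit.

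**People affected if month 52 were enforced.** Only those enrolled by month 40 (40 + 12 = 52) would be covered. With even accrual:

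- 38 months: 330 × 2/38 = 17.4 people (5.3%).
- 39 months: 330 × 3/39 = 25.4 people (7.7%).

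**12-month N, with 80% contact among the rest.**

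- Plan: 0.80 × 330 = 264, as the SAP states.
- 38 months: 0.80 × (330 − 17.4) = 250.1.
- 39 months: 0.80 × (330 − 25.4) = 243.7.

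**Power.** Two-sample t test, equal groups, N − 2 degrees of freedom, noncentrality = d × √(N/4).

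| N | Noncentrality | Power |
|---|---|---|
| 264 | 2.84 | .809 (SAP: .82) |
| 250.1 | 2.77 | .787 |
| 243.7 | 2.73 | .777 |

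The first row comes close to the SAP's own figure. The fair comparison is .81 against .78–.79, all from the same formula and all without allowance for clustering by house.

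**The case against.** The strongest defence is that the Timeline is a planning calendar. It cancels no interview, while the protocol explicitly requires all of them. The last row gives a window for completing the analysis and does not say that the 12-month analysis must begin in month 53. Two or three months can be absorbed before month 60. All of this stands, so the loss of participants and power is conditional. It does not remove the contradiction, because no text says that interviews continue past month 52.

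It is also fair to say that late enrollees would still contribute baseline and 6-month data. The SAP describes its 264 as people with two or more time points. Any loss would therefore be confined to the 12-month time point.

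A reader might infer more than the documents support:

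- **That the protocol's recruitment period contradicts the SAP's and is the one that fits.** The protocol's 3 years is a round figure in a remark on feasibility. Taken as exactly 36 months and counted inclusively, it ends in month 40 and meets month 52 with no slack. With labels read as points in time, 5 + 36 + 12 = 53 and it does not fit.
- **That the pace cannot reach the target.** 8 × 38 = 304, but the SAP gives 8 as approximate, and 330/39 = 8.46 rounds to it (330/38 = 8.68 does not). This is a rounding point.
- **That the 12 months run from house entry.** This would shrink the gap by up to a month. The Design Summary makes baseline the first of the three time points in the year, and Structure of MICM Sessions ties 12 months to study enrolment. Both point to baseline or enrolment.
- **That the clustering-adjusted sample size falls too.** That calculation concerns an average over three interviews, and the people affected would still supply two of them. Removing them altogether would overstate the loss.

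**Conclusion.** The Timeline is wrong as written. Its close of follow-up comes 2–3 months before the last required 12-month interviews, on either reading of the recruitment row and with follow-up timed from baseline.

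The statistical consequence is modest and arises only if month 52 is enforced. In that case 5–8% of participants would have no 12-month interview, and unadjusted power at d = .35 would drop by 2–3 percentage points. Those figures assume even accrual to 330 and 80% contact among everyone whose interview falls within the window. A reader might infer that data will be lost or that the arm comparison is biased. The documents do not support this: they require every interview, and nothing links the shortfall to study condition.

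**What to change.** Change the follow-up row of the SAP Timeline to end at month 54, or at month 55 if enrolment continues through month 43. State that the final 12-month analysis is done only when those interviews are complete. No participants are added, and the study stays within 60 months.

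The cost is time. The 8 months for analysis and writing (53–60) become 6 (55–60) or 5 (56–60). Interviewing, and the monthly MICM contacts that the protocol already specifies for 12 months after enrolment, would run 2–3 months beyond the present close.

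The alternative is to close recruitment at month 40. That needs 330/36 = 9.2 participants per month, about 15% above the stated 8 (at 8 per month, 36 months gives 288). It also leaves no slack for the hard-to-reach participants whom the protocol plans to trace. The first option is the easier one to meet.

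In the same edit, align the recruitment period in the protocol's Sample Characteristics section with the SAP, and give a monthly pace that reaches 330 over the chosen period.
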